### **3.1.9 Concomitant medications and therapies**

Medications will be classified as prior, or concomitant as follows:

- Prior medication: Defined as those medications that were taken and stopped prior to the date of first dose of study treatment.
- Concomitant medication: Defined as those medications taken at any time on or after the day of the first dose of study treatment.
- Prohibited medication: Concomitant medications assessed as disallowed by the medical review as specified in CSP section 6.5.2.

A medication started prior to the first dose of study treatment and ended after the first dose or is ongoing will be classified as both prior and concomitant. All records, including those

collected during the follow-up period as well as prior to the first IP administration will be considered and summarised.

### **3.2 Primary efficacy variables**

The primary efficacy variable is the change in weekly average of daily NRS pain scores from baseline to Week 12.

The NRS is an 11-point Likert scale used to assess pain, where participants are asked to describe their average pain in the target knee by identifying a number from 0 = “no pain” to 10 = “most severe pain imaginable over the previous 24 hours”. This will be recorded on a daily basis at approximately the same time every morning. The daily NRS pain scores will be recorded via electronic patient recorded outcome (ePRO) diary.

The relevant visit associated with the daily NRS scores will be derived based on the date of NRS pain scores that coincide with the relevant visit date as recorded on the electronic case report form (eCRF). Therefore, the Week 12 weekly average of daily NRS pain scores is the average of the daily NRS pain scores of 7 days up to and including the date on which the week 12 (EOT/ET) visit occurred.

For participants that discontinue the treatment period, the date of the ET visit as recorded on the eCRF in form of the week 12 (EOT/ET) visit will be associated with the protocol defined visit based on the study day, and the 7-day average for that specific visit will be derived using the same approach as described above for the Week 12 average. If the ET visit coincides with the target study day of the EOT visit, then this ET average will not be derived as it cannot represent a valid Week 12 average. In other words, only participants that complete the treatment will have Week 12 average derived. For those who prematurely withdraw from the treatment the Week 12 average will be imputed. At least four of the seven daily scores need to be recorded by the participant to obtain a weekly average value including baseline for the statistical analyses.

If there are less than four daily scores for the Week 12 average due to an inappropriate visiting schedule of Week 11 (Week 11 and Week 12 in close succession), the derivation of the Week 12 average will take priority over the Week 11 average. The weekly average will be derived in the same manner as described above but daily scores that may have been used for derivation of the Week 11 average would instead be used for derivation of the Week 12 average to ensure that at least 4 scores are available.

For the primary endpoint, an attributable estimand strategy will be adopted for missing or unevaluable data accounted for by any of the defined intercurrent events. Missing or unevaluable primary endpoint values will be imputed, but the method of imputation will differ depending upon the intercurrent event, as detailed in [Table 2](#) below.

Primary endpoint data missing due to other reasons than those summarised in [Table 2](#) will be imputed using missing-at-random (MAR) multiple imputation approach, as outlined in section [4.1.1.1](#).

In addition, only single LOCF imputation will be applied as specified in section [4.1.1.1](#).

Unevaluable data of the primary and key secondary variables are defined as cases where:

- Participant’s cumulative daily dose of rescue medication of at least 4000 mg or prohibited pain medication were taken for a minimum of 4 days over the 7-day period that is being considered for deriving the weekly NRS average. In this instance the NRS average will be set to missing.
- Participant’s cumulative daily dose of rescue medication of at least 4000 mg was taken within 24h prior of the WOMAC and PGA assessment or prohibited pain medication was taken a day before the WOMAC and PGA assessment. In this instance the WOMAC and PGA score is set to missing.

In addition, all daily NRS scores affected by use of prohibited pain medication or paracetamol intake of cumulative daily dose of at least 4000 mg will be set to missing and not used for derivation of the weekly averages.

Furthermore, there is potential for unevaluable primary and key secondary variable data in cases where prohibited pain medication was taken for less than 4 days over the 7-day period that is being considered for deriving the weekly NRS average or more than one day prior to WOMAC or PGA assessment.

Participants with potentially unevaluable data will be reviewed prior to study unblinding by the study team who will confirm whether the data is deemed unevaluable or not. Only evaluable data for such participants will be included in the analyses.

**Table 2 Intercurrent events and imputation strategy**

Intercurrent event	Single imputation strategy (Used for tabulation purposes)	Multiple imputation strategy (Used for formal analyses)
Discontinuation due to lack of efficacy or an AE	Missing data imputed assuming an unfavourable outcome, that is the BOCF imputation	MNAR: BOCF approach
Taking prohibited pain medication during the treatment period	Data affected will be set to missing and then imputed assuming an	

Taking excessive permitted rescue medication	unfavourable outcome, that is the BOCF imputation	
Discontinuation due to other reasons such as loss to follow-up or external circumstances	Missing data imputed assuming missing at random, that is the LOCF imputation	MAR approach

BOCF, baseline-observation-carried-forward; LOCF, last-observation-carried-forward; MAR, missing at random; MNAR, missing not at random.

More details concerning the imputation of missing or unevaluable primary endpoint data can be found in section [4.1.1.1](#).

### 3.3 Secondary efficacy variables

The following are the key secondary efficacy endpoints:

- Change in the WOMAC pain subscale from baseline to Week 12
- Change in the WOMAC physical function subscale from baseline to Week 12
- Change in the PGA of OA from baseline to Week 12

The same attributable estimand strategy as well as single LOCF imputation as for the primary efficacy endpoint will be applied for these key secondary efficacy endpoints. In addition, missing Week 12 WOMAC pain subscale scores will be imputed using a differing MI approach as described in section [4.1.1.1](#)., as a supportive analysis to compare with previously published studies.

The other secondary efficacy endpoints are summarised in section [1.1.2](#). However, data of all available per protocol visits will be used for analysis and summarised (Weeks 2, 4, 6, 8, 10, 12 and 18) unless otherwise specified.

Finally, the ET assessments of all secondary endpoints will be handled in the same manner as for primary endpoint that is will be reassigned based on the study day.

#### 3.3.1 WOMAC multiscale index

The Western Ontario and McMaster Universities Osteoarthritis (WOMAC) multiscale index is used to assess pain, stiffness, and joint functionality in the past 48 hours in participants with OA of the knee or hip. The WOMAC questionnaire will be completed for the target knee at Visit 2 (Week 0, baseline), Visit 4 (Week 2), Visit 5 (Week 4), Visit 6 (Week 6), Visit 7 (Week 8), Visit 8 (Week 10), Visit 11 (EOT or ET Week 12) and Visit 12 (Week 18) for only those participants who complete the treatment period. On dosing days, the WOMAC questionnaire will be completed prior to IP administration.

### **3.3.1.1 WOMAC pain subscale**

The WOMAC pain subscale consists of 5 questions assessing the participant's pain due to OA in the target knee. Each question is scored on an NRS scale from 0 to 10, where higher scores represent higher pain. The WOMAC pain subscale score is calculated as the mean score from all 5 questions.

### **3.3.1.2 WOMAC physical function subscale**

The WOMAC physical function (PF) subscale consists of 17 questions assessing the participant's difficulty in performing activities of daily living due to OA in the target knee. Each question is scored on an NRS scale from 0 to 10, and the WOMAC PF subscale score is calculated as the mean score from all 17 questions, where higher scores represent worse function.

### **3.3.1.3 WOMAC stiffness subscale**

The WOMAC stiffness function subscale consists of 2 questions assessing stiffness due to OA in the target knee. Stiffness is defined as a sensation of decreased ease of movement in the target knee. Each question is scored on an NRS scale from 0 to 10, and the WOMAC stiffness function subscale score is calculated as the mean score from the 2 questions, where higher scores represent higher stiffness.

### **3.3.1.4 WOMAC overall score**

The WOMAC overall score consists of all 24 questions reported in the WOMAC questionnaire to assess: i) pain subscale, ii) PF subscale and iii) stiffness subscale. WOMAC overall score is calculated as the mean score from all 24 questions where higher scores represent worse outcome.

## **3.3.2 Patient's Global Assessment (PGA) of Osteoarthritis (OA)**

The PGA of OA is a 5-point Likert scale used to assess symptoms and activity impairment due to OA of the knee. Participants are asked to identify a number from 1 = "very good (asymptomatic and no limitation to normal activities)" to 5 = "very poor (very severe symptoms which are intolerable and inability to carry out all normal activities)" based on the question "Considering all the ways that OA of the knee affects you, how are you feeling today?". The PGA questionnaire will be administered at the time points specified in the CSP (Refer to CSP Table 1). Participants who discontinue IP early will have their last PGA of OA assessment at the ET visit. On dosing days, the PGA assessment will be completed prior to IP administration.

## **3.3.3 OMERACT-OARSI responder index**

The OMERACT-OARSI responder index is calculated from the WOMAC Pain subscale, the WOMAC Physical Function Subscale and the PGA of OA. A participant is classified as a responder if either of the below occurs:

1.  $\geq 2$ -point absolute change from Baseline to Week X or a  $\geq 50\%$  improvement is reported in the WOMAC Pain or the Physical Function subscales.
2. At least 2 of the following 3 conditions are true:
  - $\geq 1$ -point absolute change from Baseline to Week X or  $\geq 20\%$  improvement is reported in the WOMAC Pain subscale.
  - $\geq 1$ -point absolute change from Baseline to Week X or  $\geq 20\%$  improvement is reported in the WOMAC Physical Function subscale.
  - $\geq 1$ -point absolute change from Baseline to Week X is reported in the PGA of OA.

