### 1.1.2 Secondary objectives

Secondary Objectives	Estimand descriptions/endpoints

To assess the efficacy of MEDI7352 compared to placebo on additional measures of efficacy in participants with painful OA of the knee
	
Key secondary endpoints:
 
 
• Change in the WOMAC pain subscale from baseline to Week 12
 
• Change in the WOMAC physical function subscale from baseline to Week 12
 
• Change in the PGA of OA from baseline to Week 12
 
 
Other secondary endpoints:
 
 
• Change in the WOMAC pain subscale from baseline to Weeks 2, 4, 6, 8, 10, and 18
 
• Change in the WOMAC physical function subscale from baseline to Weeks 2, 4, 6, 8, 10, and 18
 
• Change in the WOMAC overall scores from baseline to Weeks 2, 4, 6, 8, 10, 12, and 18
 
• Change in the WOMAC stiffness scores from baseline to Weeks 2, 4, 6, 8, 10, 12, and 18
 
• Change in PGA of OA from baseline to Weeks 2, 4, 8, 10, and 18
 
• Percentage of responders as measured by the OARSI responder index using the OMERACT-OARSI definition (Pham et al 2004) at Weeks 2, 4, 8, 12, and 18
 
• Percentage of participants who have achieved an improvement of <math>\geq 2</math> points in PGA of OA at Weeks 2, 4, 8, 12, and 18
 
• Change in the weekly average of daily NRS pain scores from baseline to Weeks 2, 4, 6, 8, 10, and 18
 
• Percentage of participants who have achieved <math>\geq 30\%</math> and <math>\geq 50\%</math> reductions in the weekly average of daily NRS pain scores from baseline to Weeks 2, 4, 8, 12, and 18
 
• Percentage of participants who have achieved <math>\geq 30\%</math> and <math>\geq 50\%</math>, reductions in WOMAC pain subscale scores at Weeks 2, 4, 8, 12, and 18.
 
• Percentage of participants who have achieved <math>\geq 30\%</math> and <math>\geq 50\%</math> reductions in WOMAC physical function subscale at Weeks 2, 4, 8, 12, and 18
 

To assess the PK of MEDI7352 in participants with painful OA of the knee
	
 
• Serum concentration of MEDI7352
 

Secondary Objectives	Estimand descriptions/endpoints
To assess immunogenicity of MEDI7352 in participants with painful OA of the knee	
 
• Presence of ADA to MEDI7352
 
• ADA titre
 

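### The OMERACT-OARSI point thresholds have no direction, so a worsening participant meets the rule as written, and the 'or' makes the percentage thresholds redundant at higher baselines

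*SAP*

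**What the plan says.** Section 1.1.2 lists, among the other secondary endpoints, the percentage of responders on the "OARSI responder index using the OMERACT-OARSI definition", with a literature citation. Section 3.3.3 writes the rule out. A participant responds by meeting either of two criteria.

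- **Criterion 1:** a 2-"point absolute change from Baseline to Week X or a" 50% "improvement is reported in the WOMAC Pain or the Physical Function subscales".
- **Criterion 2:** "At least 2 of the following 3 conditions are true". The pain condition is a 1-point absolute change or a 20% "improvement is reported in the WOMAC Pain subscale". The function condition has the same form. The third condition is a 1-"point absolute change from Baseline to Week X is reported in the PGA of OA", with no percentage part.

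The scales run the same way. For WOMAC pain (3.3.1.1), "Each question is scored on an NRS scale from 0 to 10, where higher scores represent higher pain". For physical function (3.3.1.2), the score is a 0 to 10 mean "where higher scores represent worse function". PGA (3.3.2) runs from 1, very good, to 5, very poor. Section 3.1.3 defines change as the post-baseline value minus baseline, and expresses percent change for the primary and key secondary endpoints as improvement.

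**The concern.** There are two separate problems in one definition.

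**Direction.** 'Improvement' is attached to the percentages and to nothing else. If 'absolute change' means magnitude, a worsening of the same size qualifies. If it means the signed change of section 3.1.3, a change of at least 2 is a worsening and nothing else. On neither reading does the written rule exclude a participant who got worse, and no other section gives this index a direction.

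**Connective.** With 'or', the easier of the two thresholds decides. On a 0 to 10 scale that is the point threshold once baseline is high enough, so the 50% and 20% figures stop mattering there.

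At stake is an endpoint for which section 4.2.2 reports responder percentages, odds ratios, confidence intervals and nominal p-values by week. Misclassified worsening does not raise every arm equally. It adds most responders where true improvement is smallest, so it dilutes the comparison with placebo.

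**Working it through.** The SAP gives no responder rate for this index, so there is no planned figure to reproduce. Three checks follow.

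**1. The rule applied to single participants** (other components unchanged)

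- Pain 7 to 9: the magnitude of change is 2, so criterion 1 is met as written. It is not met if improvement is required.
- Pain and function both 6 to 7: two magnitudes of 1, so criterion 2 is met as written. It is not met if improvement is required.
- Pain 5 to 4 (1 point, 20%) with PGA worsening from 3 to 4: criterion 2 is met as written, with the worsened PGA supplying the second condition. Changing 'or' to 'and' would not cure this case, because the PGA condition has no percentage part.

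**2. Where 'or' makes the percentage redundant** (B is the baseline score)

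- 50% of B is at least 2 points when 0.5 × B ≥ 2, that is B ≥ 4.
- 20% of B is at least 1 point when 0.2 × B ≥ 1, that is B ≥ 5.
- At B = 7, 2 points is 2/7 = 28.6% and 1 point is 1/7 = 14.3%. Both pass.
- All attainable scores were enumerated (pain in steps of 1/5, function in steps of 1/17). The highest baselines at which the 50% threshold admits anyone extra are 3.6 (pain) and 3.88 (function). For the 20% threshold they are 4.0 and 4.71.
- Below those values the percentages do act. Pain 3.0 to 1.4 is 1.6 points, or 53%, and responds only through the percentage.

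**3. Illustrative size**

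All inputs here are assumptions, because the SAP gives no WOMAC baseline distribution. Pain baseline has mean 7 and SD 1.2, and pain change has SD 2.0. Function changes track pain changes (0.8 times the pain change plus noise of SD 0.9, with the same mean). PGA baseline is 3 to 5, and PGA change is 0.3 times the pain change plus noise of SD 0.6, rounded. There are 40,000 simulated participants per scenario, with scores clipped to their scales. Responders (%):

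| Mean improvement | 'or', either direction | 'or', improvement only | 'and', improvement only |
|---|---|---|---|
| 0 | 58.5 | 29.3 | 22.9 |
| 1.5 | 69.7 | 60.0 | 51.0 |
| 2.5 | 82.1 | 78.3 | 70.7 |

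For direction, the contrast between mean improvements of 1.5 and 2.5 is 78.3 − 60.0 = 18.3 points if only improvement counts, and 82.1 − 69.7 = 12.4 points if either direction counts. Between 0 and 2.5 it is 49.0 against 23.6 points. Over assumed baseline means of 4 to 8, counting either direction adds 24.4 to 30.5 points at zero mean change and 3.3 to 4.2 points at 2.5 points' improvement.

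For the connective, with improvement only, the percentage limbs under 'or' add 3.6 to 4.5 points over the point thresholds alone at baseline mean 4, 1.3 to 1.7 at mean 5, at most 0.5 at mean 6, and about 0 at means 7 and 8. At mean 7, 'or' gives 6.4 to 9.0 points more responders than 'and', but the contrast between 0 and 2.5 barely moves (49.0 against 47.8).

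**The case against.** The best defence on direction is that this is drafting. 'Absolute change' set beside a percentage may simply mean points as opposed to percent, the label is 'responder', and the separate PGA endpoint in section 1.1.2 does say improvement. A sensible programmer would probably code a decrease. That bears on how likely the error is, and a reader should not infer that the trial's code counts worsening: the SAP does not show this derivation. It does not rescue the written rule, which leaves the direction to inference.

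The defence on the connective is stronger, and much of it stands. 'Or' is a coherent rule, in which points govern high baselines and percentages govern low ones. Three stronger readings are tempting and not supported:

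- A reader might infer that the percentage thresholds do nothing at all. They admit extra responders below baselines 4 and 5, and the SAP states no minimum WOMAC score. A simulation that truncates baseline at 4 would show no effect of the 50% threshold by construction.
- A reader might infer that 'or' is wrong and must be 'and'. The cited definition is not reproduced in the SAP, and nothing in the SAP contradicts 'or'.
- A reader might infer that the results would not be comparable with other trials. That rests on the same unseen source.

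The endpoint is also minor. It is one of eleven listed other secondary endpoints, is analysed on observed cases, lies outside hypotheses H1 to H10, and is not a criterion in either interim decision.

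**Conclusion.** Wrong as written. The point thresholds of section 3.3.3, and the whole PGA condition, admit participants who worsen. This follows from the text and the scale definitions alone. If the rule were coded literally, it would add most false responders where true improvement is smallest and so shrink treatment contrasts, for example from 18.3 to 12.4 points under the assumptions shown. The direction of that effect held at every baseline mean tried. The exact sizes depend on assumed distributions.

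The redundancy of the percentages is exact arithmetic: from baseline 4 for 50%, and from baseline 5 for 20%. That probably covers most of a moderate-to-severe population, but the share cannot be computed from the SAP. Whether 'or' is the intended connective is open until the cited definition is consulted.

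The primary endpoint, the key secondary endpoints and type I error control are not affected.

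**What to change.** - In both criteria, replace the undirected wording with an improvement, meaning a decrease from baseline, of at least the stated number of points. Do this for WOMAC pain, WOMAC physical function and PGA.
- Because section 1.1.2 says the endpoint uses the cited definition, reconcile the connective with that source before the derivation is programmed, or check the code if it already exists. Change 'or' to 'and' if the source requires both thresholds. If 'or' is deliberate, say so.

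The direction fix costs one line of SAP text and a check of one derivation. It changes no result if a decrease was already coded. If the connective changes to 'and', responder percentages can only fall or stay the same, by 6.4 to 9.0 points in the baseline-7 illustration. No sample size or testing strategy is touched.

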### 3.4 Pharmacokinetic and immunogenicity variables

Blood samples for PK and ADA assessments will be analysed by bioanalytical test sites. All serum samples will be collected prior to study treatment administration (on dosing days) at the time points specified (See CSP Table 1). On non-dosing days, PK and ADA samples will be collected in the morning and the time of sample collection must be recorded. Note that participants who discontinue IP early will have their last PK sampling at the ET visit.

#### 3.4.1 Pharmacokinetics

The serum MEDI7352 concentrations will be determined only for participants randomised to an active treatment.

At a visit/time point for a specific cohort where less than or equal to 50% of the concentration values are not quantifiable (NQ) that is are below the lower limit of quantification (LLOQ), all such values will be set equal to the LLOQ value, and all descriptive statistics will be calculated accordingly (using the value of the LLOQ that will be included in the summary statistics).

At a visit/time point for a specific cohort where more than 50% (but not all) of the values are NQ, the gmean,  $\text{gmean} \pm \text{gSD}$  and gCV% will be set to NC. The maximum value will be reported from the individual data, and the minimum and median will be set to NQ.

If all concentrations are NQ for a specific cohort at a visit/time point, no descriptive statistics will be calculated for that time point. The gmean, minimum, median and maximum will be reported as NQ and the gCV% and  $\text{gmean} \pm \text{gSD}$  as NC.

#### 3.4.2 Immunogenicity

For immunogenicity analysis, the presence of detectable (i.e., positive) anti-drug antibodies (ADAs) against MEDI7352 will be reported. ADA results from each sample are reported as either positive or negative. In addition, the ADA titer result will be reported for samples confirmed positive for the presence of ADAs. A participant is defined as being ADA-positive

if at least one positive ADA result is available at any time (including baseline and all post-baseline measurements); otherwise ADA negative.

The following ADA categories will be determined:

- **ADA positive** if a collected sample is tested positive at any time during the study, including baseline and/or post-baseline. (The percentage of these participants in a population is known as ADA prevalence)
- **Treatment-emergent ADA positive (TE-ADA+)**: A positive post-baseline result and either of the following statements holds:
  - Baseline is ADA negative and at least one post-baseline assessment is ADA positive. This is called **treatment-induced ADA positive**.
  - Baseline is ADA positive, and the baseline titre is boosted by greater than the variability of the assay (i.e.  $\geq X$ -fold increase, commonly 4-fold) at  $\geq 1$  post-baseline timepoint. This is called **treatment-boosted ADA positive**.  
(The percentage of these participants in a population is known as **ADA incidence**)
- **Non-Treatment-emergent ADA positive (non-TE-ADA+)**: Participants who are ADA positive but not fulfilling the conditions for TE-ADA+
- **Treatment-emergent Persistently ADA positive**: ADA negative at baseline and having at least 2 post-baseline ADA positive measurements with  $\geq 16$  weeks (112 days) between first and last positive, or an ADA positive result at the last available post-baseline assessment
- **Treatment-emergent Transiently ADA positive**: ADA negative at baseline and at least one post-baseline ADA positive measurement and not fulfilling the conditions for persistently positive
- ADA positive post-baseline and positive at baseline.
- ADA not detected post-baseline and positive at baseline.

ADA evaluable participants are defined as the participants in the safety analysis set who have a non-missing baseline and at least one non-missing post-baseline ADA results.

